Study Title: A Health System Wide Evaluation of Mandated Use and Clinical Decision

Support Tools to Improve PDMP Utilization and Patient Outcomes

NCT Number: NCT04918355

Document Date: 3 December 2021

COMIRB Protocol

COLORADO MULTIPLE INSTITUTIONAL REVIEW BOARD
[name]
[contact] [contact]

Protocol #: **19-1130**

Project Title: A Health System Wide Evaluation of Mandated Use and Clinical Decision Support Tools to Improve PDMP Utilization and Patient Outcomes

Principal Investigator: [name], DO

Version Date: 3 December 2021

I. Hypotheses and Specific Aims:

Prior research by this team has shown that when emergency department (ED) prescribers are less likely to prescribe an opioid analgesic to patients at high-risk of overdose or misuse when they consult the Colorado Prescription Drug Monitoring Program (PDMP). Despite extensive work to reduce workflow and accessibility barriers to use of the PDMP, the majority of providers still do not use the PDMP when making prescription decisions. Clinical decision support (CDS) that is embedded in the Electronic Health Record (EHR) has promise as a tool to increase PDMP use, advance presentation of important PDMP data to providers and improve opioid safety without interrupting provider workflow.

This cluster-randomized study is designed to determine if:

- CDS tools that deliver focused, timely clinical information to prescribers can improve use of the PDMP
- The use of focused CDS tools can decrease high-risk opioid prescribing
- The use of focused CDS tools is associated with better patient outcomes: decreasing high-risk, long-term, and aberrant opioid use

Specifically, we will test the hypotheses that:

[figure not shown]
1. Use of a focused CDS tool will increase the percentage of high-risk patients who are checked in the PDMP in the target populations, compared to those who have not implemented the tool.
2. Use of a focused CDS tool will decrease the percentage of high-risk patients who receive a controlled medication prescription in the target populations, compared to those who have not implemented the tool.

II. Background and Significance:

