issue, the current study will focus on designing, testing and implementing CDS tools to ensure delivery of the right PDMP information to prescribers at the right time within their workflow to increase compliance with the recommended best practice of PDMP review.

IV. Research Methods

A. Outcome Measure(s):

Primary outcome:

- Changes in the percentage of high-risk patients (patients who are flagged by the CDS logic) who are checked in the PDMP

Secondary outcomes:

- Changes in the percentage of high-risk patients (patients who are flagged by the CDS logic) who receive a controlled medication prescription
- Overall utilization of the PDMP prior to prescribing for low risk/naïve patients vs. high risk patients
- Percentage of patients who receive a controlled medication prescription who go on to long- term or aberrant use of controlled medication when CDS is used vs. controls

B. Description of Population to be Enrolled:

Two distinct populations will be involved in this study.

1. Health care providers licensed to prescribe opioid analgesics in the UCHealth system. These individuals will use CDS tools provided in the course of normal clinical care and have the opportunity for qualitative feedback on tools. We will collect de-identified data on CDS use and prescribing practices of providers. There will be no attempts to link qualitative responses with measures of prescribing practices, which will be measured system wide as described elsewhere. Oncology, hospice/palliative care, and pediatric practices will be excluded

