2. Patients seeking care in the UCHealth system, who may receive an opioid prescription. The population will be limited to non-prisoners 12-89 years of age. Individuals with an active cancer diagnosis, sickle cell disease, or receiving specific end of life care are excluded. Pregnant women and decisionally challenged people will be included but are not considered a target population. No efforts will be made to include these individuals. Patients with limited literacy or limited English fluency will be included but are not considered a target population. Juveniles seen at providers included in the specialties of interest will be included (ages 12-17 inclusive) due to the inclusion of their health care provider. On the advice of pediatric toxicology experts, a cut point of 12 years of age is a clinically relevant age at which misuse of opioid analgesics and other controlled medications becomes a notable risk. However, no efforts will be made to target or enhance inclusion of juveniles. Pediatrics-only specialist offices will not be included in rollout of the CDS tools. Outcomes measures from juveniles will be examined separately from adults but may be included in the overall population if statistically appropriate.

C. Study Design and Research Methods

This will be a 1) cluster-randomized (by practice, as identified by a group of providers who work in the same department or set of departments within UCHealth) study for ambulatory/outpatient providers and 2) a randomized study (by provider) for emergency medicine and inpatient providers, with four study arms:

1. Arm 1: No change in practice
 - Providers are free to access the PDMP when prescribing via the existing integrated PDMP button.
 - This control group will enable monitoring of the secular changes in rates of controlled medication prescription within the UCHealth system.
 - In order to facilitate analysis of patient outcomes, CDS logic as in group 4 will run “silently” in this group such that risks are identified and recorded but not seen by the provider.
2. Arm 2: “Mandatory” use of the PDMP for all opioid prescriptions.
 - A best practice alert (BPA) will be triggered and fire when ordering an opioid prescription. The BPA will not appear (i.e. it will be suppressed) if the provider already reviewed the PDMP within the encounter. The BPA is shown in Figure 2 below.

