 - Although this condition is termed “mandatory” use, it is not a hard stop. The provider can easily close the window without consulting the PDMP and the prescription can be signed whether the PDMP has been consulted or not. The BPA will be built to track utilization of the BPA vs. bypass. Note: This has been deemed too interruptive for

[figure not shown]

Figure 2: Example BPA used in prior study.

ambulatory clinics and they will not be included in this arm.

3. Arm 3: CDS for high risk patients based on PDMP data
 - Based on initial interviews with providers (see 19-3063) CDS support will be designed to be supportive of provider workflows via interruptive alerts (BPAs) for high-risk patients only. No alerts will fire for patients without high risk indicators based on data in the PDMP or prescription history as shown in Epic. An example is given below. Exact phrasing may be modified during final testing in order to streamline appearance of the alert.
 - Again, BPA will be triggered upon entry of an opioid or benzodiazepine prescription and will fire only for patients determined to be at risk for controlled medication associated adverse events, misuse or overdose, based on logic built to identify high-risk characteristics. Definition of these risk characteristics is based on CDC guidelines and include: NarxCare opioid or overall overdose risk score (PDMP based) indicating the patient is in the highest ~5% of the population for controlled medication risk, initiating opioid treatment with an extended or long acting release formulation with no opioid usage in the previous 100 days, or information in the PDMP or EHR indicating overlapping opioid use or co-prescribing of a sedative with an opioid.
 - One-click access to the PDMP for all patients will be maintained as in other arms. If the provider reviews the PDMP during the encounter before prescribing, the BPA will be suppressed.

- As in Group 2, this is not a truly mandatory check and can be bypassed. BPA messaging was determined based on work with providers to deliver the most useful and clear information.
- The text displayed in the alert will be specific to the patient. BPA logic and phrasing is included in Appendix A.

[figure not shown]

Figure 3: Sample alert.

4. Arm 4: CDS for high risk patients based on PDMP and/or clinical characteristics

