- Prescribers will be stratified based on primary work site. As a number of facilities within the UCHealth system share staff, "work site" is being defined based on shared staffing as follows:

Emergency Department(s)	Hospital/Inpatient facilities
UCHospital at AMC	UCHospital at AMC

Broomfield Hospital; Commerce City, Green Valley, Littleton, Mississippi, Parker, Ralston freestanding EDs	Broomfield Hospital
Highlands Ranch Hospital	Highlands Ranch Hospital
Memorial Hospital North, Memorial Hospital Central, Pikes Peak Regional, Grandview Hospital; Fountain, Meadows, Powers, Woodmen freestanding EDs	Memorial Hospital North, Memorial Hospital Central, Pikes Peak Regional, Grandview Hospital
Greeley Hospital, Longs Peak Hospital, Medical Center of the Rockies, Poudre Valley Hospital, Harmony freestanding	Greeley Hospital, Longs Peak Hospital, Medical Center of the Rockies, Poudre Valley Hospital
Estes Park Hospital	Estes Park Hospital
Yampa Valley Medical Center	Yampa Valley Medical Center

- Prescribers will be randomized at the time of activation of the CDS using permuted block randomization base upon their primary work site and will remain in study for 12 months.
- CDS will only fire for discharge prescriptions (i.e. not for inpatient orders) for prescribers working in hospital-based facilities.
- Providers who work in multiple locations will be assigned to the location where they do the majority of their prescribing.

Primary care and selected specialty practices

- Practices will be randomized into study arms 1, 3, or 4. Due to workflow concerns and the longitudinal physician/patient relationship in primary care, and based on feedback from primary care leadership, inclusion of an interruptive, non-specific alert was considered to be counterproductive in this population.
- Practices will be stratified as small, medium, or large based on the number of opioid and benzodiazepine prescriptions written in the year prior to randomization. Small practices are those with a number of prescriptions in the lowest third, large practices in the highest third, and medium size practice all others.
- Practices with less than 52 total opioid plus benzodiazepine prescriptions in the year prior to randomization will be excluded. With less than one prescription per week, the impact of the CDS on prescribing is anticipated to be minimal and excluding such low providers will reduce the risk of inactive prescribers biasing results.

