- Practices will be randomized at the time of activation of the CDS and will remain on study for 12 months.

Practices may be added during the course of the study. Follow up for patient outcomes will continue for 6 months following deactivation of the alerts.

CDS tools will be activated first in EDs, then for inpatient providers, and finally in ambulatory settings. This staged roll out will allow for identification and modification of system bugs and unanticipated problems, as well as allow for increased socialization of the tools and greater buy in by providers.

This study design is chosen for a combination of scientific and pragmatic concerns. This study is effectively an implementation of a novel CDS augmentation, such as would happen routinely in a non-research environment on a practice-by-practice basis. Therefore, to better mimic this real world situation, the most appropriate unit of randomization would be the practice/site. However, pragmatic concerns also inform the design, specifically:

- 1. Primary care:** Randomizing by practice will optimize the opportunities for provider education and reduce the risk of cross-group contamination if a single provider or practice treated multiple patients with similar risk patterns but received different CDS alerts. It also ensures that all members of a treatment team working with a single patient or single encounter receive the same information about that patient's risk stratification.
- 2. Hospital based:** The small number of EDs and hospitals, especially large EDs, relative to the number of randomization groups translates to a large risk of unbalanced groups. To address this issue, a smaller unit of randomization is appropriate specifically for EDs and hospital discharges. The authorizing provider is ultimately responsible for opioid prescribing and as such is most appropriate as a smaller unit. As residents work under a number of attending physicians, this will also prevent the development of overreliance on automated alerts in a physician in training, in order to minimize the chance of risk to clinical care.

Prior to CDS activation and at the time of activation, training materials will be shared with relevant sites and practices. These materials are included in Appendix #. A link to a provider feedback survey in REDCap will be included in order to collect standardized feedback from system users.

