Survey responses	See draft included with submission	Provide ideas of aspects of CDS tool considered worthwhile by users. Descriptive statistics only, non-quantitative analysis.

[#]All data will be deidentified prior to release of data to the research team.

G. Summarize Knowledge to be Gained:

As PDMP use improves prescribing decisions, this study will provide immediate, direct benefit to study participants. Further, it will provide greater understanding of the reasons why clinicians use or do not use the PDMP as recommended, and explore several options for improving utilization and maximizing appropriate clinician use of the information provided. Finally, it will explore patient focused outcomes when the PDMP is used (or not), and if patient outcomes are better (defined as less aberrant or long term opioid use) when PDMP CDS tools are better integrated into the provider's workflow and better focused on providing high impact, risk based information

to the provider at the appropriate time. Given the number of patients and providers covered by the UCHealth system, and the geographic dispersion of UCHealth facilities around the state, it is likely that results will be generalizable through the state and other states through the region. The degree to which our findings will be generalizable beyond Colorado and the mountain west regions is uncertain.

H. References:

- [5] Vestal C. Overdose Deaths Fall in 14 States, Vol. 2019: Pew Trust, 2018.
- [6] Ingalls J. More than 1,000 Coloradans Lost to Drug Overdoses in 2017, Vol. 2019: Colorado Health Institute, 2018.

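### Long-term or aberrant use is compared only among patients who receive a controlled prescription, an event after randomisation that the CDS is meant to reduce; the bias can run either way

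*Combined protocol and SAP*

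**What the plan says.** Section IV.A lists as the third secondary outcome the "Percentage of patients who receive a controlled medication prescription who go on to" long-term or aberrant use of controlled medication, contrasting CDS use with controls. It does not say whether receipt means in the study encounter or from any source.

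Randomisation comes earlier. Section IV.C states for ED and inpatient staff that "Prescribers will be randomized at the time of activation of the CDS", and for clinics that "Practices will be randomized at the time of activation of the CDS". Hypothesis 2 in section I is that "Use of a focused CDS tool will decrease the percentage of high-risk patients who receive a controlled medication prescription in the target populations", and the first secondary outcome measures the same thing.

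The aim is wider than the measure. Section I describes better patient outcomes as "decreasing high-risk, long-term, and aberrant opioid use". Section G says the study will explore whether "patient outcomes are better (defined as less aberrant or long term opioid use". Neither is limited to recipients.

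Section IV.F lists the patient measures, including prescriptions inside and outside UCHealth, but gives no other denominator, model or adjustment for this outcome. The only related handling rule is in section IV.E: censor at a subsequent visit and restart follow-up.

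**The concern.** The denominator is a post-randomisation event on the intended causal path. If the CDS changes who is prescribed, recipients in the CDS and control arms are differently selected, and a difference in their later use mixes that selection with any effect on use.

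The alert rules make uneven selection plausible. In arm 2, "A best practice alert (BPA) will be triggered and fire when ordering an opioid prescription"; in arm 3, "No alerts will fire for patients without high risk indicators based on data in the PDMP" or the prescription history. The preliminary study in section III points the same way: the odds of an opioid prescription fell with each prior fill when the PDMP was searched (OR 0.92) and not when it was unsearched (OR 1.01). That compares searched with unsearched patients in an earlier ED study, so it supports plausibility and says nothing about size here.

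At stake is one of the three study questions in section I, in the phase that section IV.F says drives enrolment. A patient spared a prescription, the obvious route to benefit, is not counted at all.

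**Working it through.** The plan states no rate, effect or power for this outcome, so there is no figure to reproduce. The check is a two-group mixture. All inputs are assumptions unless a source is given.

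**Set-up.** h = higher-risk share of eligible patients (0.30); pH, pL = risk of long-term use in higher- and lower-risk patients (0.25, 0.05); rH, rL = receipt in each group (0.60 in control).

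- Recipients R = h·rH + (1−h)·rL
- Cases among recipients C = h·rH·pH + (1−h)·rL·pL
- Planned percentage = C / R

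Control: R = 0.600, C = 0.0660, planned percentage 11.0%.

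**1. Receipt in the study encounter falls only in higher-risk patients; no patient's later use changes.** Use over all eligible patients is 0.30×0.25 + 0.70×0.05 = 11.0% in both arms.

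| rH | R | C | Planned % | Relative change |
|---|---|---|---|---|
| 0.60 | 0.600 | 0.0660 | 11.0 | – |
| 0.55 | 0.585 | 0.06225 | 10.6 | −3.3% |
| 0.40 | 0.540 | 0.0510 | 9.4 | −14.1% |

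Varying pH over 15–40% at rH = 0.55, the false relative fall is 1.3% to 4.1% for a higher-risk share of 10–50%. For a share of 5%, the section IV.C cut for the NarxCare score, it is 0.7% to 2.1%. Since the alert criteria go beyond that score, 5% is a lower anchor.

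**2. Receipt counts from any source, and only the unprescribed patients who go on obtain outside prescriptions.** Cases are then 0.11 in both arms.

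- Control: recipients 0.600 + 0.40×0.30×0.25 + 0.40×0.70×0.05 = 0.644; 0.11/0.644 = 17.1%.
- rH = 0.55: recipients 0.585 + 0.45×0.30×0.25 + 0.014 = 0.63275; 17.4%.
- rH = 0.40: recipients 0.540 + 0.60×0.30×0.25 + 0.014 = 0.599; 18.4%.

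This is a false rise from the same change in prescribing. If instead every averted patient obtains a prescription elsewhere, the shift disappears.

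**3. Receipt falls evenly to 0.48; averted patients do not go on.** R = 0.480, C = 0.0528, planned percentage 11.0%, unchanged. Use per eligible patient falls from 6.6% to 5.3%, a 20% reduction that the planned percentage does not show.

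**4. Lower-risk prescriptions are averted, with real benefit.** Take would-be recipients as the base: 15% higher-risk, pH = 0.30, pL = 0.05, and 20% of lower-risk prescriptions averted in patients who then do not go on. Control is 8.75%. With CDS, cases are 0.15×0.30 + 0.68×0.05 = 0.079 and recipients 0.15 + 0.68 = 0.83, giving 9.52%. The recipients-only ratio is 1.088 (apparent harm); over all would-be recipients it is 0.079/0.0875 = 0.903 (benefit).

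**The case against.** The best defence is that the plan collects what is needed to see the problem. Section IV.C describes a third-level silent alert that records risk in every arm for use in the final analysis, and section IV.F collects patient characteristics. In scenario 1 the risk-specific percentages stay at 25% and 5%, so stratifying would expose the case-mix shift. This stands as mitigation. No such analysis is stated, though, and the alert does not set this denominator.

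The first secondary outcome would also reveal a fall in receipt. In scenario 3, receipt times the recipients-only percentage (0.48 × 11.0% = 5.3%) recovers the per-eligible figure. That works only if averted patients do not go on, and the two outcomes use different populations: flagged patients for one, all recipients for the other.

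The size may be small. If every higher-risk patient were searched, the OR of 0.92 would need about 2.5 prior prescriptions to move receipt from 60% to 55%: ln[(0.55/0.45)/1.5]/ln(0.92). If half were searched it would need about 4.9, and at section III's check probability of 0.218 about 11.2. This is a fair limit on magnitude and leaves the structural point untouched.

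Finally, the outcome is secondary, and neither numbered hypothesis tests it. That limits its weight.

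**Conclusion.** The concern holds and should be fixed. Followed as written, the third secondary outcome is a non-randomised comparison on a denominator the CDS is expected to change, and it does not measure the aim stated in sections I and G. Confidence is high on this structure and low on magnitude, because every rate in the illustration is assumed.

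A reader might infer that the planned comparison flatters the CDS. The documents do not support a direction. The false fall needs receipt to mean the study encounter; an any-source reading can give a false rise; and a real benefit can appear as no change or as harm.

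A reader might also infer from Figure 4, where the third-level alert mirrors an alert triggered by a controlled prescription, that the hypothesis 2 percentage is itself biased. That is not established. The accompanying text says the alert fires for all eligible patients seen, and section IV.F says each patient record is queried automatically. The text and figure need reconciling here only because they decide whether silent-alert data exist without an order.

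**What to change.** 1. Make the main comparison of long-term or aberrant use by randomised arm, not by whether the CDS was used (the present wording allows either reading). Take all eligible patients seen by randomised units, indexed at the first eligible encounter after activation. State in advance how an encounter without an order is linked to a randomised unit. Use the section IV.E censor-and-restart approach as a sensitivity analysis.
2. Report the same comparison in patients who are high-risk on criteria that need no order: NarxCare score, overlap already on record, EHR history.
3. Keep the recipients-only percentage as descriptive, stratified by recorded risk, and define receipt (study encounter or any source).
4. Reconcile the section IV.C text on the third-level silent alert with Figure 4.

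The alert logic is unchanged. The cost is analysis wording and a wider retrospective extract. Section IV.F already counts all queried individuals as participants, but the extract criteria in section IV.C are not shown, so coverage of non-recipients cannot be assumed.

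The all-eligible comparison is diluted. Section IV.F's counts give 290,000/906,000 = 32% receipt (opioids only, system-wide), so the percentage would be about one third of the recipients-only figure if non-recipients do not go on. The high-risk subgroup avoids much of this: on the assumed inputs, and if unprescribed patients do not go on, it gives 0.60×25% = 15.0% in control, and 13.8% or 10.0% at 55% or 40% receipt. Its risk definition is narrower than the alert's.

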In addition, a second silent alert (3rd level in model) will fire for all eligible patients seen by study providers, using the same criteria as the PDMP + EHR alert described above. As with the previously described alert, PDMP use will not suppress this alert so that all patients can be captured. This alert will allow us to document the same risk information for all study patients so we can describe patient risk information across intervention groups. Much of this information tends to be transient and variable over time. Having a snapshot of the data at that moment will be valuable in the final analysis.

Intervention→ Purpose ↓	Provider Group 1: Control (no alert)	Provider Group 2: "Mandated"	Provider Group 3: PDMP	Provider Group 4 [CN1] PDMP + EHR
1 st level: Visible alert		
VISIBLE 14118
 
 Trigger: controlled rx PDMP attestation suppresses: yes 	
VISIBLE 14643
 
 Trigger: controlled rx, + PDMP criteria PDMP attestation suppresses: yes 	
VISIBLE 14644
 
 Trigger: controlled rx, + PDMP and/or + EHR PDMP attestation suppresses: yes
2 nd level: Capture all PDMP use (silent)		
SILENT
 
 Trigger: Mirror of 14118 PDMP attestation suppresses: No 	
SILENT
 
 Trigger: Mirror of 14643 PDMP attestation suppresses: no 	
3 rd level: Capture full patient risk profile (silent)	
SILENT
 
 Trigger: Mirror of 14644 PDMP attestation suppresses: no 	
SILENT
 
 Trigger: Mirror of 14644 PDMP attestation suppresses: no 	
SILENT
 
 Trigger: Mirror of 14644 PDMP attestation suppresses: no 	
SILENT
 
 Trigger: Mirror of 14644 PDMP attestation suppresses: no

Figure 4: Visible (top row) and silent alerts used in the study CDS

Due to primary care not allowing interruptive BPAs, there will be two units of randomization corresponding to the ED/hospital discharge and the outpatient care setting, respectively.

Prescribers working in UCHealth Emergency Departments and inpatient facilities

- Each ED/inpatient prescriber will be randomized to one of the four study arms described above. Dentists will be excluded.

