Provider identifying information will be retained in order to determine the effectiveness of the educational outreach. Information retained will include alert firings (including multiple firings/patient) and provider actions over time. In order to better understand the environments in which educational intervention is most effective, provider specialty, primary work site, and basic demographic information (age, gender, race/ethnicity), will be obtained from within the EHR. Method of notification (email or internal messaging within the EHR) will also be tracked to compare provider behavioral changes between educational notifications. Provider work environment (Emergency Department, inpatient or ambulatory) will be determined based on study randomization lists. Data will be deidentified for analysis. Data on CDS and site performance will be monitored continuously during the course of the study (see attached file "Baseline data" for details of data monitored) via automated data extract built by ED Epic analytics team and monitored by study team. No identifiable data will be collected in order to protect confidentiality. De-identified extracts of these data may be exported from Epic to the UCDenver OneDrive system for CDS monitoring and analysis. Baseline data will be gathered retrospectively for the 12 months prior to first deployment of the CDS for each randomization unit. Providers who are not in the system for the baseline will be excluded from analysis.

Validation of the alerts

In order to ensure that the alerts are functioning properly prior to activation, up to 30 individual firings will be identified by study staff and EHR records of the patient will be checked to confirm that a controlled medication was prescribed and the risk criteria identified by the alert system are reflected in the medical record. Records of this validation will be maintained only by alert firing number. Identifying information associated with the alert will not be maintained once the alert firing is validated.

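### A provider-level baseline rule applied at analysis drops randomised ED/inpatient prescribers and some patients of randomised practices, which costs precision and system-wide scope but does not bias the arms

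*Combined protocol and SAP*

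**What the plan says.** The rule is in Section IV.C (Study Design and Research Methods), at the end of the paragraph on provider and monitoring data, just before the validation of the alerts: "Providers who are not in the system for the baseline will be excluded from analysis". The sentence before it defines the baseline: "Baseline data will be gathered retrospectively for the 12 months prior to first deployment of the CDS for each randomization unit".

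The randomisation rules, also in Section IV.C, are these:

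- **ED and inpatient.** "Each ED/inpatient prescriber will be randomized to one of the four study arms described above". Dentists are excluded. On timing, "Prescribers will be randomized at the time of activation of the CDS", in permuted blocks by primary work site, with 12 months on study.
- **Ambulatory.** "Practices will be randomized into study arms 1, 3, or 4", and "Practices will be randomized at the time of activation of the CDS and will remain on study for 12 months". A practice must have written at least 52 opioid plus benzodiazepine prescriptions in the year before randomisation. In addition, "Practices may be added during the course of the study".

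Neither list requires an individual provider to have been present during the baseline year. Section IV.F (Data Analysis Plan) defines no as-randomised set, no other analysis set, and no sensitivity analysis that would bring the excluded providers back.

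**The concern.** A criterion that does not govern entry to randomisation decides who is analysed. An ED prescriber hired a month before activation is allocated to an arm, may see alerts for a year, and then contributes nothing. A physician who is new to an ambulatory practice works under that practice's allocation, yet that physician's patients leave the analysis while colleagues' patients stay. The rule acts on the provider although the randomised unit is the practice and the plan itself counts baseline back from each unit's deployment.

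At stake are precision and the population to which the result applies. The title promises a health-system-wide evaluation, and Section IV.E (Potential Scientific Problems) wants the tools spread over as many providers as can be reached, so that secular trend and study effect can be separated. The primary outcome in Section IV.A concerns the percentage of flagged patients checked in the PDMP, and the two hypotheses in Section I are comparisons with those who have not implemented the tool. A between-arm comparison of that kind does not need a personal baseline for every provider.

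**Working it through.** **Figures in the plan.** None bears on this point. Section IV.F bases enrolment on patient counts rather than on a power calculation. The plan gives no turnover rate, number of randomised units or intracluster correlation (ICC), so there is no stated figure to reproduce. What follows illustrates size under assumptions.

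**Step 1. Who is removed.**

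| Provider | Randomised? | Analysed under the rule? |
|---|---|---|
| ED/inpatient, present at activation, with baseline | Yes, individually | Yes |
| ED/inpatient, present at activation, no baseline | Yes, individually | No: a randomised unit is lost |
| Ambulatory, present at activation, no baseline | Through the practice | No: the practice stays, this provider's patients go |
| Ambulatory, joins after activation | Enters a practice already allocated | No |

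The plan does not say whether ED/inpatient prescribers hired after activation are randomised at all.

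**Step 2. Bias.** For anyone present at activation, presence in the baseline year is settled before allocation, and the rule is the same in every arm. Removing these providers cannot depend on arm. It may disturb balance within blocks by chance. Joining a practice after activation is different, because it follows allocation.

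**Step 3. Precision, ED/inpatient.** Let t be the share of prescribers lacking a baseline (assumed), with prescribers equally informative. The standard error is multiplied by 1/√(1 − t):

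- t = 0.10: 1/√0.90 = 1.054, up 5.4%
- t = 0.20: 1/√0.80 = 1.118, up 11.8%
- t = 0.30: 1/√0.70 = 1.195, up 19.5%

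**Step 4. Precision, ambulatory.** The number of practices is fixed and patients per practice fall from m to m(1 − t). The multiplier is √{[1 + (m(1 − t) − 1)·ICC] / [(1 − t)(1 + (m − 1)·ICC)]}. I assume m from 52 to 500 and ICC from 0.01 to 0.10. At t = 0.20 the two ends are:

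- m = 52, ICC = 0.01: √[1.406 / (0.8 × 1.51)] = √(1.406/1.208) = 1.079, up 7.9%
- m = 500, ICC = 0.10: √[40.9 / (0.8 × 50.9)] = √(40.9/40.72) = 1.002, up 0.2%

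Over the same grid, the range is 0.1% to 3.6% at t = 0.10 and 0.4% to 13.2% at t = 0.30.

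**Step 5. Loss of a whole practice.** A practice with J providers disappears only if all of them lack a baseline. With independence, that chance is t^J. At t = 0.20 it is 4% for two providers, 0.8% for three and 0.03% for five.

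**The case against.** The best defence is that the rule has a purpose. The primary outcome is worded as a change, and Section IV.F tracks provider rates over time; a provider without a baseline cannot show a change from it. The rule is also the same in all arms and, for those present at activation, amounts to an eligibility criterion stated late. This stands as a reason to keep a baseline-present set for change summaries. It does not justify making that set the only one.

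A second defence concerns scope. The sentence closes a paragraph that begins with educational outreach and monitoring data, so it may not have been meant for every outcome. The wording has no such limit, however, and it directly follows the definition of baseline for each randomisation unit. If only outreach was meant, the plan should say so.

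Three stronger readings are tempting, and the documents do not support them:

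- **That randomised practices are routinely lost.** They are not; see Step 5. Only the ED/inpatient stratum loses randomised units as a matter of course.
- **That a practice added mid-study would be randomised and then wholly discarded.** Its baseline is the "12 months prior to first deployment of the CDS for each randomization unit", so late entry does not itself trigger the exclusion, and the 52-prescription threshold requires prior-year activity. A practice new to the system whose providers have no records might be caught, but the plan describes no such case and does not state where the prescription counts come from.
- **That newer prescribers would respond differently to the alerts.** Nothing in the documents addresses this. The point about scope needs only that they are left out.

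**Conclusion.** The point holds as a loss of precision and scope, not as bias between arms. As written, the plan randomises providers without a baseline, individually or through their practice, and then drops them, and no other analysis set retains them. In ED/inpatient care the standard error would rise by about 5% if 10% lack a baseline and by about 20% if 30% do. Those shares are assumptions, and this range must not be carried over to ambulatory care, where the loss is smaller for the same share. The conclusion would then apply to established staff only.

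How many providers are affected depends on an undefined phrase: being in the system for the baseline could mean any part of the 12 months or all of it, and the second reading removes anyone hired during that year. This should be changed because the remedy is cheap and needs no new data.

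**What to change.** Replace the sentence in Section IV.C, and set out the analysis sets in Section IV.F as follows:

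1. The primary analysis keeps every prescriber present at activation, in the arm to which the prescriber or the practice was randomised.
2. In ED/inpatient care, adjust for the prescriber's baseline rate. Where there is none, fill in a constant and add a missing-baseline indicator; this is valid here because the missingness predates randomisation.
3. In ambulatory care, adjust for the practice's own baseline rate and keep the encounters of all members present at activation.
4. Report the baseline-present set as a sensitivity analysis, with excluded providers and patients counted by arm. Define what presence in the baseline means and which analyses the restriction covers.
5. State in advance whether providers who join a practice after activation belong to the primary or a sensitivity set. Including them matches the practice as the unit; excluding them avoids selection after allocation. Either is defensible.

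The cost is a few sentences. Because Section IV.F names no primary model, the baseline-adjusted model has to be written down as well. The downside is that prescribers without a baseline gain less from the adjustment and cannot enter provider-level change-from-baseline summaries.
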